### **Dose interruptions**

In the case an interruption takes place during the *individual dose titration period* and lasts longer than 3 consecutive days (9 doses missed), it is not allowed to restart the study medication again (respective subjects must be withdrawn from the trial).

In case an interruption takes place after completion of the titration period and lasts longer than 14 consecutive days, it is not allowed to restart the study medication again. In case of shorter interruptions, study medication can be restarted at the discretion of the investigator. Dose interruptions will be communicated to the DMC and/or SC.

*(Note: The dose titration algorithm, dose up-titration in the LTE phase, and wording under dose interruptions were clarified according to Amendment 9, see Sections [17.4.1.10](#), [17.4.1.6](#) and [17.4.1.9](#).)*

## **5.2 Subject identification**

At screening Visit 0 and after having obtained informed consent and, if applicable, child assent has been provided, each subject will be assigned a unique 9-digit subject identification (SID) number by IxRS for unambiguous identification. The first 2 digits represent the country

code, the next 3 digits represent the center code, and the last 4 digits represent a sequential number assigned to each subject.

Subject identification numbers must be used in sequence and no number should be skipped, substituted or re-used.

### **5.3 Duration of study treatment - amended**

During the individual dose titration period with a maximum duration of 8 weeks, the individual maximum equivalent dose will be established. Subjects will be treated on this body-weight adjusted dose level during the 16-week maintenance period as long as well tolerated. Subjects who have completed 24 weeks of treatment will be offered participation in the Long Term Extension (LTE) phase.

*(Note: Wording describing the LTE in this section was modified according to Amendment 3, see Section 17.1.1.1.)*

### **5.4 Formulation and dose - amended**

Riociguat will be provided by Bayer as film-coated tablets and granules for reconstitution in an oral suspension (0.15 mg/mL), see [Table 5-1](#). The following tablet strength will be available: 0.5 mg, 1.0 mg, 1.5 mg, 2.0 mg, and 2.5 mg. For the application of the oral suspension, two sizes of dosing pipettes, manufactured by Raumedic, which are considered medical devices (therefore also called LDD- Liquid Dosing Device), are available and certified. These dosing pipettes are designed to deliver between 1 mL and 5 mL with 0.25 mL dosing increments as well as 2 mL to 10 mL with 0.5 mL dosing increments. These increments were chosen to enable accurate bodyweight-adjusted dosing. Further details on the dose-measuring pipettes for the oral suspension formulation are given in detail in the suspension manual.

Tablets and oral suspension will be administered orally in a TID regimen.

Subjects <50 kg at baseline will receive riociguat oral suspension during the initial 24-week treatment phase.

Subjects  $\geq$ 50 kg at baseline will receive oral tablets. If the BW decreases below 50 kg, then the IXRS will deliver the oral suspension.

During the long-term extension phase, subjects receiving stable dose of 1.0 mg, 1.5 mg, 2.0 mg, or 2.5 mg TID as oral suspension, can switch to the tablet formulation according to the discretion of the investigator provided the body weight is  $\geq$  50 kg (for details on tablet and suspension body-weight adjusted equivalent dosing, see [Table 5-2](#).)

*(Note: The text was modified according to Amendment 3, see Section 17.1.1.13.)*

**Table 5–1: Identity of investigational product**

International non-proprietary name (INN)	Riociguat	
Sponsor's internal reference number	BAY 63-2521	
Formulation	Film-coated tablets	Oral suspension
Galenical form	Round immediate-released tablets, diameter 6 mm	Granules
Composition	
Active ingredient: Methyl-N-[4,6-diamino-2-[1-[(2-fluorophenyl)methyl]-1H-pyrazolo[3,4-b]pyridin-3-yl]-5-pyrimidinyl]-N-methyl-carbaminate
 
Empirical formula: C20H19FN8O2
 
Molar mass: 422.42 g/mol (molarity)
 
Excipients: lactose, microcrystalline cellulose, magnesium stearate, crospovidone, hypromellose, and sodium lauryl sulphate
 
Coating: hydroxypropyl cellulose, hypromellose, propylene glycol, iron oxide (red and yellow), and titanium dioxide.
	
Strength	0.5 mg, 1.0 mg, 1.5 mg, 2.0 mg, and 2.5 mg	0.15 mg/mL
Material numbers	83296470 BAY 63-2521 TABL 0.5 mg 511 COAT 83296535 BAY 63-2521 TABL 1.0 mg 512 COAT 83296543 BAY 63-2521 TABL 1.5 mg 513 COAT 83296578 BAY 63-2521 TABL 2.0 mg 504 COAT 83296608 BAY 63-2521 TABL 2.5 mg 515 COAT	84367923 BAY 63-2521 GRAN SUSP 0.3%
Packaging	High-density polyethylene bottles	Brown glass bottles

Abbreviation: TABL = tablet

All subjects will receive body-weight-adjusted dose of riociguat. The starting dose will be the body weight-adjusted equivalent of the 1.0-mg dose in adults. Guidelines on how to prepare the oral suspension are provided to the subjects/parents.

The body-weight-adjusted riociguat dosing schedule is provided in [Table 5–2](#).

**Table 5–2 : Body weight-adjusted riociguat dosing schedule**

Body weight (kg)	0.5 mg equivalent TID (mg)/	equivalent volume of suspension TID (mL)*	1.0 mg equivalent TID (mg)	equivalent volume of suspension TID (mL)*	1.5 mg equivalent TID (mg)	equivalent volume of suspension TID (mL)*	2.0 mg equivalent TID (mg)	equivalent volume of suspension TID (mL)*	2.5 mg equivalent TID (mg)	equivalent volume of suspension TID (mL)*
≥12<14	0.12	1.0	0.25	1.75	0.37	2.50	0.50	3.25	0.62	4.25
≥14 <16	0.14	1.0	0.28	1.75	0.42	2.75	0.56	3.75	0.70	4.75
≥16 <18	0.15	1.0	0.31	2.00	0.46	3.00	0.62	4.25	0.77	5.00
≥18 <20	0.17	1.0	0.33	2.25	0.50	3.25	0.67	4.50	0.83	5.50
≥20 <25	0.19	1.25	0.38	2.50	0.57	3.75	0.75	5.00	0.94	6.50
≥25 <30	0.22	1.50	0.44	3.00	0.66	4.25	0.87	6.00	1.09	7.50
≥30 <35	0.25	1.75	0.50	3.25	0.74	5.00	0.99	6.50	1.24	8.50
≥35 <40	0.28	1.75	0.56	3.75	0.84	5.50	1.12	7.50	1.41	9.50
≥40 <50	0.33	2.25	0.66	4.50	1.00	6.50	1.33	9.00	1.66	11.00
≥ 50	0.50	3.25	1.00	6.50	1.50	10.00	2.00**	13.50	2.50**	16.50

Abbreviations: TID = three times daily

\* For facilitation of administration of a proper body-adjusted dose, the volumes of suspension are provided with increments of 0.25 mL (for 1-5 mL) and 0.5 ml (for over 5 ml)

\*\* For change in weight category from 40-<50 kg to ≥ 50 kg, IXRS will administer intermediate dose to adjust to 0.5 mg increment (e.g. intermediate dose for 2.0 mg equivalent is 1.50 mg /10.00 mL; for 2.5 mg equivalent is 2.00 mg / 13.50 mL).

*(Note: The table was modified according to Amendment 3, see Section 17.1.1.6.)*

## 5.5 Packaging, labeling, and storage

All study medication will be labeled according to local law and legislation. Also, a system of numbering in accordance with Good Manufacturing Practice (GMP) will be used, ensuring that each dose of study medication can be traced back to the respective bulk ware of the ingredients. Further details are provided in a separate manual.

A complete record of batch numbers and expiry dates of all study medication provided by Bayer, as well as the labels, will be maintained in the study file.

All study medication need to be stored at the site according to the labeled storage advice in accordance with Good Clinical Practice (GCP) and GMP requirements.

The study drug is to be kept in a secure area. The responsible site personnel will confirm receipt of study medication via IxRS and will use the study medication only for this study and in accordance with this protocol. Receipt, distribution, return and destruction (if any) of the study medication must be properly documented according to specified procedures.

## 5.6 Treatment assignment - amended

After enrolment, the subject identification number will be recorded on the corresponding electronic case report form (eCRF). The subject identification number will also have to be recorded on the label of the study medication.

In case bosentan or other ERA and/or PCA is/are provided locally, the compound's name, dose, quantity and batch number, or a copy of the prescription has to be included in the subject's files.

*(Note: The text was modified according to Amendment 3, see Section 17.1.1.11. The text was modified according to Amendment 6, see Section 17.3.1.9.)*

## 5.7 Study treatment delivery and compliance assessment

All empty packaging and unused study drug will be returned at all study visits. All non-used study medication will be kept securely in a designated locked container. Tablets and suspension volumes will be counted for a compliance check. The investigator should ensure adequate subject compliance.

# 6. Study procedures

## 6.1 Study visits - amended

The main study part comprises 3 periods:

- Pre-treatment period (Screening): up to 2 weeks. This period is to identify potential eligibility of subjects who have been diagnosed with PAH. This visit will take place up to 2 weeks before Visit 1 (baseline visit).
- Main study (Active) treatment period: 24 weeks (titration phase: 8 weeks, maintenance phase: 16 weeks):
  - The individual titration phase comprises 4 visits 2 weeks ( $\pm 2$  days) apart.
  - The maintenance phase comprises 5 visits 4 weeks ( $\pm 5$  days) apart.

- Follow-up period: at least 60 days for serious adverse events (SAEs). (Only for patients who do not enter the long-term extension study or who stop the study medication prematurely.)

Subjects who have completed 24 weeks of treatment will be offered participation in an optional long term extension phase. Subjects not entering the LTE phase will perform the safety follow-up visit (see section 6.1.4). Subjects completing the optional LTE will also perform the safety follow up visit after 60 + 8 days after LTE. Subjects dropping-off the protocol any time after Visit 1 and before Visit 9 will perform an end-of-treatment visit (see section 6.1.3).

The titration visits have to be performed at the study site. Only visits at Week 12 and/or Week 20 (Visit 6 and/or Visit 8) might be performed as home visits by an experienced nurse/ healthcare practitioner in close contact with the treating investigator, when no further titration is scheduled and subjects are on stable dose. The decision to delegate the responsibility to visit the subject is at the discretion of the investigator, must be consistent with regional medical practice, and in accordance with regional legal requirements. The responsibility must be documented on the delegation log and signed by the investigator. At the end of the titration phase (Week 8, Visit 5) patients will have reached riociguat doses between 0.5 mg TID and 2.5 mg TID.

*(Note: The wording describing LTE was modified according to the Amendment 3, see Section 17.1.1.1. The Section was modified according to Amendment 6, see Section 17.3.1.2.)*

### **6.1.1 Pre-treatment phase (Visit 0, Day -14 to -1) - amended**

The parents/legal guardians and children will be given an explanation about the study and will be given sufficient time to consider their participation in the study and to ask any questions. Afterwards, informed consent and, if applicable, assent will be obtained (see section 11.2). Collection of AEs starts after informed consent is signed. If the subject passes the screen of inclusion and exclusion criteria, the subject will be eligible to enter the study. The following procedures will be performed if no historical data (not older than 30 days) are available:

- Obtain demographics (incl. smoking status) and medical history
- Record concomitant PAH specific medication
- Perform physical examination (incl. height, weight, vital signs and pubertal assessment using Tanner scale [see section 18.3])
- Obtain blood sample if AST, ALT, creatinine, blood urea nitrogen (BUN), gamma-glutamyltransferase (GGT), uric acid (UA), total bilirubin (T-Bil), Albumin (Alb), Sodium (Na), potassium (K), Calcium (Ca), P and complete blood count (CBC) are not available within 30 days prior to screening visit
- Perform ECG (electrocardiogram)
- Pregnancy test for females of childbearing potential
- Child Health Questionnaire (SF-10 and PedsQL Generic Core Scales self-report) (section 18.2 and 18.7)
- In case RHC has been performed for a study subject before enrollment, record the most recent RHC parameters to the eCRF (timing of RHC not limited to the period of Day -14 to -1)

*(Note: The text was modified according to Amendment 3, see Sections 17.1.1.8 and 17.1.1.16. The Section was modified according to Amendment 5, see Sections 17.2.1.1 and 17.2.1.2. The Section was modified according to Amendment 6, see Sections 17.3.1.2 and 17.3.1.3. The Section was modified according to Amendment 9, see Section 17.4.1.8.)*

## **6.1.2 Main study treatment period - amended**

### **6.1.2.1 Individual titration phase (Visit 1 – Visit 4) - amended**

At Visit 1, subjects should come to the hospital for the riociguat morning dose. At Visits 2 and 4, subjects are allowed to take the riociguat morning dose up to midday. The following procedures will be performed during the titration period:

- Procedures and assessments for the baseline visit (Visit 1) should be completed within the span of one day
- Re-confirm in-/exclusion criteria (Visit 1 only, prior to study drug intake)
- Record concomitant medication incl. concomitant PAH specific medication
- Perform physical examination (incl. height, weight and vital signs)
- Pregnancy test for females of childbearing potential (at Visit 1 and Visit 3)
- Decide on the next dose based on the titration algorithm and dispense study medication
  - Instruct how to take study drug
  - Provide study guidelines for dosing/suspension (Visit 1 only)
- Determine WHO functional class (Visit 1 only)
- Perform echocardiogram (Visit 1 only)
- Perform electrocardiogram (Visit 1 only)
- X-ray of left hand for determination of bone age (Visit 1 only: if no historical data [not older than 30 days] are available)
- Perform 6MWD test (Visit 1 only)
- Collect PK sample (Visit 1 and 3), for details see [Table 0–2](#)
- Collect NT-proBNP or BNP (Visit 1 only; when both tests are available, NT-proBNP should be chosen over BNP and the same test should be performed at every required visit)
- Check adverse events including adverse events of special interest
- Check the systolic BP monitoring form provided by the patients at the visit, if applicable (Visit 2 – 4)
- Check drug accountability (Visit 2 – 4)
- Taste assessment questionnaire (Visit 1 only) (section [18.4](#))
- Record laboratory parameters (AST, ALT, BUN, creatinine, GGT, UA, T-Bil, Alb, Na, K, Ca, P, and CBC) to eCRF when obtained as medically required according to a

local package insert of bosentan or other ERA, or medical practice at the study site at any time.

- In case RHC is conducted based on medical reasons during the study, record RHC parameters to eCRF

*(Note: The Section was modified according to Amendment 3, see Sections 17.1.1.8 and 17.1.1.16. The Section was modified according to Amendment 5, see Sections 17.2.1.1 and 17.2.1.2. The section was modified according to Amendment 6, see Sections 17.3.1.2 and 17.3.1.6. The section was modified according to Amendment 9, see Section 17.4.1.5.)*

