### 3.1 Study description - amended

After providing written informed consent and assent (if applicable) subjects will undergo a screening evaluation to determine their eligibility. Eligible subjects – once on stable background treatment with PAH medications (ERA and/or PCA) - will start body-weight adjusted individual dose titration (IDT) regimen as described in section 5.1.1. After the individual titration phase of maximum of 8 weeks, subjects will enter the 16-week maintenance phase. The last dose administered at Visit 4 will be regarded as individual optimal dose and subject will receive that treatment during the maintenance phase.

Subjects of the older age cohort ( $\geq 12$  to  $< 18$  years) will be treated first. After 5 patients of this age cohort have reached their optimal dose and received this dose until assessment of their first control x-ray of left hand at week 24, an independent Data Monitoring Committee (DMC) will give recommendations to the Steering Committee (SC) whether to continue with enrolment in this age cohort and open enrollment in the subsequent lower age cohort ( $\geq 6$  to  $< 12$  years).

Children who require treatment with riociguat for more than 24 weeks will be offered participation in an extension study and continuation until market approval of riociguat for the

pediatric population or until they are 18 years of age (whatever comes first). Subjects reaching adulthood can be transitioned to commercially-available Adempas.

The primary objective is the evaluation of safety and tolerability as well as the pharmacokinetic properties of riociguat in the pediatric population. The DMC will monitor the subjects' safety on an ongoing basis and give recommendations to the SC.

For all subjects, visits are scheduled at regular time points (see [Table 0-1](#)). Subjects who prematurely discontinue study drug or do not consent to participate in the long-term extension phase will be seen at the safety follow-up visit. During all contacts, the treatment and clinical course of the subject will be evaluated. Subjects with suspected safety concerns (for safety outcomes see section [6.2](#)) will undergo confirmatory testing as per standard of care. Blood samples for PK will be taken at defined time points (see [Table 0-2](#)).

The reason why subjects did not pass the screen of in- and exclusion criteria after obtaining informed consent/child assent will be documented.

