At each titration visit, the individual dose will be assigned based on the following algorithm where peripheral systolic blood pressure (SBP) will be measured (by oscillometry with the same calibrated oscillometry unit in each center) at trough before intake of the first dose of the day.

*(Note: The description of the dosing of riociguat was clarified according to Amendment 3, see Sections 17.1.1.6, 17.1.1.13, and 17.1.1.16. The Section wording was modified according to Amendment 5, see Section 17.2.1.8. The Section was modified according to Amendment 6, see Section 17.3.1.2.)*

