## 6.4 Pharmacokinetics/Pharmacodynamics analyses - amended

Blood samples will be taken for pharmacokinetic and pharmacodynamic measurements from all participants treated with riociguat.

The number of PK blood samples to be taken has been optimized using physiologically based pharmacokinetic (PBPK) modelling predictions in conjunction with clinical trials simulations (CTS) in order to only collect the minimum amount of blood needed for adequate analysis (sparse sampling).

Based on these evaluations the following measures to minimize pain and distress have been included: the number of blood samples in children from 6 to less than 18 years of age for PK analysis must not exceed four, and the minimum amount of blood needed for adequate analysis of each sample is 1.0mL of blood.

The following blood samples will be taken:

**Visit 1:** 2 PK samples will be taken: the first at 0.5 to 1.5 h and the second at 2.5 to 4 h post-dose. Preferred proposal is to have both post-dose samples at the first visit. (To ensure having PK samples in case of drop-outs, both “early post-dose” samples should be collected at the first visit. If this is not feasible, the second post-dose sample can be taken at any visit.)

**Visit 3 and Visit 5:** Trough samples should be collected -1 to 0 hours before the morning dose at both visit 3 and visit 5, which is approx. 5 to 15h after the evening dose.

For all visits in the main study phase, the exact time of three riociguat dosings (current and the previous two doses) and time of PK blood sampling will be documented in the eCRF.

If, for any reason, PK samples are taken outside of the pre-specified time window, the exact time that the sample was taken should be recorded and not the pre-defined time window. If riociguat was temporarily stopped prior to a PK sample collection visit, sampling of blood for PK analysis according to this visit's schedule should be postponed until riociguat treatment has been restarted and sustained for 3 days.

If PK samples are collected at an unscheduled visit or at a visit not foreseeing PK collection, the previous riociguat doses and the time of sampling should be documented like described above. Those samples may be included in the analysis.

Primary PK outcome measure:

Pre- and post-dose blood samples for PK characterization of riociguat and its active metabolite BAY 60-4552 will be collected during the titration and the maintenance phase of the study. For details, see section 7.4.3.

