### **17.4.1.5 Modification 5: Change to allow dose to be taken at midday during the visits without PK sampling**

Since, as per in the protocol, PK samples are not required to be taken at Visit 2 and 4, subjects were allowed to take the morning dose of the study drug until midday.

After Visit 1, PK blood sampling occurs at Visits 3 and 5, for which patients are required to come to the hospital without having taken the riociguat morning dose.

It has been noticed that the same requirement is kept in the study protocol at Visits 2 and 4 although no PK sampling takes place. In the amendment this requirement only applies to Visits 3 and 5, where in the visits without PK sampling it is allowed to take the morning dose until midday.

The protocol sections affected by this modification are:

[6.1.2.1 Individual titration phase \(Visit 1 – Visit 4\)](#)

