#### **17.4.2.10 6.1.2.1 Individual titration phase (Visit 1 – Visit 4)**

*Old text:*

~~At Visit 2–4, subjects should come to the hospital without having taken the riociguat morning dose. The following procedures will be performed during the titration period:~~

- Re-confirm in-/exclusion criteria (Visit 1 only, prior to study drug intake)
- ~~• Obtain medical history (Visit 1 only)~~
- Record concomitant medication incl. concomitant PAH specific medication
- Perform physical examination (incl. height, weight and vital signs)
- Pregnancy test for females of childbearing potential (at Visit 1 and Visit 3)
- Decide on the next dose based on the titration algorithm and dispense study medication
  - Instruct how to take study drug
  - Provide booklet/guidelines for dosing/suspension (Visit 1 only)
- Determine WHO functional class (Visit 1 only)
- Perform echocardiogram (Visit 1 only)
- Perform electrocardiogram (Visit 1 only)
- X-ray of left hand for determination of bone age (Visit 1 only [if no historical data ( $\leq 30$  days) are available])

[...]

*New text:*

At Visit 1, subjects should come to the hospital for the riociguat morning dose. At Visits 2 and 4, subjects are allowed to take the riociguat morning dose up to midday. The following procedures will be performed during the titration period. The following procedures will be performed during the titration period:

- Procedures and assessments for the baseline visit (Visit 1) should be completed within the span of one day
- Re-confirm in-/exclusion criteria (Visit 1 only, prior to study drug intake)
- Record concomitant medication incl. concomitant PAH specific medication
- Perform physical examination (incl. height, weight and vital signs)
- Pregnancy test for females of childbearing potential (at Visit 1 and Visit 3)
- Decide on the next dose based on the titration algorithm and dispense study medication
  - Instruct how to take study drug

- Provide study guidelines for dosing/suspension (Visit 1 only)
- Determine WHO functional class (Visit 1 only)
- Perform echocardiogram (Visit 1 only)
- Perform electrocardiogram (Visit 1 only)
- X-ray of left hand for determination of bone age (Visit 1 only: if no historical data [not older than 30 days] are available)

[...]

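### Titration depends on trough SBP, but the visit instructions for Visits 2 and 4 do not ensure that SBP is measured before the morning dose

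*Protocol*

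**What the plan says.** The titration rule is in Protocol 5.1.1: "At each titration visit, the individual dose will be assigned based on the following algorithm where peripheral systolic blood pressure (SBP) will be measured", and the reading is to be taken "at trough before intake of the first dose of the day". No visit is exempted. SAP 3.2 repeats the rule with the same timing. The algorithm compares SBP with the median for age, sex and height. The dose goes up if SBP is less than 5 mmHg below the median, stays the same from 5 to less than 10 mmHg below, and goes down at 10 mmHg or more below.

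Protocol 6.1.2.1 covers Visits 1 to 4 and instructs sites as follows: "Decide on the next dose based on the titration algorithm and dispense study medication". The same section says: "At Visits 2 and 4, subjects are allowed to take the riociguat morning dose up to midday".

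The reason is given in the Amendment 9 overview (17.4.1.5). No PK sample is drawn at Visits 2 and 4, so the rule about attending without the morning dose was narrowed: "In the amendment this requirement only applies to Visits 3 and 5". Visit 3 stays pre-dose through the PK schedule in 6.4: "Trough samples should be collected -1 to 0 hours before the morning dose at both visit 3 and visit 5".

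The Visit 4 decision carries the most weight. Protocol 3.1 states: "The last dose administered at Visit 4 will be regarded as individual optimal dose and subject will receive that treatment during the maintenance phase". Section 5.1.1 adds that a dose lowered for safety during maintenance may not be raised again in that phase.

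**The concern.** Two current sections give different signals about the same measurement. One makes the dose depend on a pre-dose reading. The other lets the child take the morning dose at any time up to midday and does not say whether the blood pressure comes first. A child who has already taken the dose at home cannot supply the reading that 5.1.1 calls for.

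By the protocol's own account, timing matters. The Amendment 9 text on cardiac output (17.4.1.7) describes a direct relationship between riociguat plasma concentration and SBP, and Visit 1 measures blood pressure pre-dose and again at 2 and 4 hours. If sites handle Visits 2 and 4 differently, the maintenance dose a child reaches could depend partly on when the child took the dose that morning. That would add an unrecorded source of variation to dose, exposure and the by-dose adverse event tables.

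**Working it through.** The plan has no figure to reproduce here: the study is descriptive and has no formal sample size calculation. The check sets the sections side by side, counts the decisions, and adds one illustration of scale.

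**1. Timing instructions by visit (current text)**

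| Visit | Titration decision | What secures a pre-dose SBP, beyond the general rule in 5.1.1 |
|---|---|---|
| 2 | yes | nothing; dose allowed up to midday (6.1.2.1) |
| 3 | yes | trough PK sample in the hour before the dose (6.4, Table 0-2) |
| 4 | yes, sets the maintenance dose | nothing; dose allowed up to midday (6.1.2.1) |

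Table 0-2 gives pre-dose timing for Visits 1, 3 and 5 only. Flow-chart footnote d sets vital-sign timing for Visit 1 only.

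**2. What was removed.** The superseded text for Visits 2 to 4, shown in 17.4.2.10, read: "subjects should come to the hospital without having taken the riociguat morning dose". It is cited only to show which instruction is gone. The conflict itself is between 5.1.1 and 6.1.2.1 as they now stand.

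**3. Number of decisions.** Going from the 1.0 mg to the 2.5 mg equivalent in 0.5 mg steps takes (2.5 − 1.0) / 0.5 = 3 increases. With Visit 4 as the end of titration (5.1.1), these fall at Visits 2, 3 and 4. Two of the three have no secured pre-dose reading.

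**4. Sensitivity of the algorithm.** Let g be the trough gap, median minus SBP, in mmHg. Suppose the post-dose reading is d mmHg lower, so the observed gap is g + d. The category changes when g lies in [5 − d, 5) or [10 − d, 10). A child exactly at the median (g = 0) moves from increase to maintain at d = 5, and to reduce at d = 10.

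The documents give neither the spread of g nor the value of d. As an illustration only, assume g is Normal with mean 0 or 3 and SD 8, 10 or 12. For mean 0, SD 10:

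- d = 2: [Φ(0.5) − Φ(0.3)] + [Φ(1.0) − Φ(0.8)] = 0.127
- d = 5: Φ(1.0) − Φ(0) = 0.341
- d = 10: Φ(1.0) − Φ(−0.5) = 0.533

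Over all six combinations of mean and SD:

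| Assumed post-dose fall | Readings that change category |
|---|---|
| 2 mmHg | 11% to 17% |
| 5 mmHg | 30% to 46% |
| 10 mmHg | 46% to 65% |

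Because d is assumed to be a fall, every change is toward a lower dose. The percentages apply to readings actually taken post-dose, not to all readings.

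**The case against.** The strongest reply is that the two sections can be followed together. Setting a latest time most naturally permits delay, since a child dosing at the usual hour would need no permission. Where the protocol wants children to arrive already dosed, as at the later maintenance visits in 6.1.2.2, it says so. Section 5.1.1 still applies to every titration visit, the SAP restates it after Amendment 9, and a site that measures SBP first complies with everything. This stands as far as it goes: compliance with both is possible. It does not settle the matter, because the stated purpose of the change was to drop the arrive-undosed requirement at Visits 2 and 4, and no current text says that SBP must come first there.

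Several further objections limit the point:

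- A reader might infer that the amendment's authors overlooked the trough rule. The documents do not show this. The same amendment edited the SBP algorithm in 5.1.1 and left the trough sentence in place. All that can be said is that the rationale mentions only PK.
- Only the maintain band is 5 mmHg wide; the increase and reduce bands are open-ended. A child far from a cut-point is unaffected by a small shift.
- The decision is not purely mechanical. Increases are left to the investigator's judgement and also take general tolerability into account, and sites check the home SBP form where applicable.
- A reader might blame this conflict for mixed dose timing in the by-visit SBP summaries (SAP 6.4.4). Those summaries claim no trough basis, and Visits 6 to 9 are dosed at home anyway.
- Part of the remedy exists: dose times are documented at all main-phase visits (6.4), and the SAP lists all protocol deviations (4.6).

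**Conclusion.** The inconsistency is real and lies in current text. Up to two of the three up-titration decisions, including the one that sets the 16-week dose, could rest on post-dose SBP. The count assumes that titration ends at Visit 4, as 3.1 and 5.1.1 state. The consequence is confined to readings taken after dosing and close enough to the 5 or 10 mmHg cut-point to change category.

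It would be tempting to conclude that two of the three decisions are affected, or that children were under-dosed. The documents support neither: they do not show that any site used a post-dose reading, and they give no post-dose fall. The percentages in the working rest entirely on assumed inputs and indicate only that the algorithm is sensitive to timing. The point merits correction because the Visit 4 decision persists through maintenance and clarification is cheap.

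**What to change.** Protocol 5.1.1, Protocol 6.1.2.1 and SAP 3.2 must be reconciled so that a single instruction governs when SBP is taken relative to the morning dose at Visits 2 and 4. Which instruction that should be is for the sponsor and its clinical advisers; no view is taken here.

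For the data, record the clock time of each titration SBP. Set against the dose times already collected under 6.4, this classifies each reading as pre-dose or post-dose. In the analysis, flag every titration decision based on a non-trough SBP and tabulate the flagged decisions by visit and by outcome (increase, maintain, reduce).

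The cost is a short protocol clarification, one time field in the eCRF if it is not already there, and one derived flag with a small descriptive table in the SAP. For children already titrated, only the flag can be added, and only where the SBP time was captured.
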